5.6 Replacement Procedures

Patients with chronic pain who prematurely discontinue from this study after randomization may be replaced to obtain 84 completers.

5.7 Removal of Patients from Therapy

A premature discontinuation will occur when a patient who signed the informed consent form ceases participation in the study, regardless of the circumstances, before the completion of the protocol. Patients can be prematurely discontinued from the study for one of the following reasons:

- Failure to meet inclusion/exclusion criteria
- Adverse event (AE)
- Insufficient therapeutic response
- Discontinuation of study medication for more than 7 days
- Protocol violation, including lack of compliance
- Withdrawal of consent

- Other reasons, such as administrative reasons or pregnancy

All patients who prematurely discontinue from the study, regardless of the cause, should undergo a final assessment.

- Those subjects who are taking medication from the 4 week supply at the time of study discontinuation will be asked to undergo in person evaluation with QST and questionnaire completion). At that in person visit they will receive the 2 week supply of medication to taper off the study drug, will be called by the study team 1-2 weeks later to assess AEs, and will be given a stamped envelope in which to return the medication bottle. If they are not willing to return to clinic they will undergo the Final Evaluation (phone visit) and will be mailed the 2 week supply of medication to taper off the study drug. Subjects will be required to return all study drug and medication bottles.
- Those subjects who are taking medication from either the 1 week or 2 week supply at the time of study discontinuation will undergo the Final Evaluation (phone visit). No taper is required. Patients will be required to return all randomized study drug.

6.0. DESIGN

6.1 Treatments Administered

The SNRI duloxetine was chosen because it is a predominantly centrally-acting analgesic with the broadest efficacy to date (in neuropathic pain, fibromyalgia, low back pain, and osteoarthritis), and the analgesic effects have consistently been shown to be independent of anti-depressive effects.^{99,100,96,101-104} SNRIs are thought to act primarily by increasing serotonin and norepinephrine transmission in the CNS, thereby augmenting and restoring pain modulation, resulting in decreased pain.⁶¹ The majority of patients who respond to duloxetine achieve a response within 2-4 weeks of initiating therapy.^{23,105} We have demonstrated the feasibility of treating cancer patients with duloxetine in trials evaluating its use for treatment of aromatase inhibitor-associated arthralgias²³ as well as chemotherapy-induced painful neuropathy.¹⁰⁶ This drug is also coming off patent soon so if these studies were to suggest efficacy in an identifiable subset of breast cancer patients, duloxetine would represent an inexpensive and safe treatment option, especially compared to the known toxicities associated with opioids and even NSAIDs.

Study drug in the form of capsules will be provided by the University of Michigan Investigational Drug Service. An IND waiver has been obtained from the US Food and Drug Administration.

6.2 Method of Assigning Patients to Treatment

All patients will receive the same treatment regardless of treatment “bin.” Approximately equal numbers of patients will be enrolled in each treatment “bin”, which are: (1) surgery +/- radiation therapy, (2) surgery and chemotherapy +/- radiation therapy, (3) surgery and endocrine therapy +/- radiation therapy, (4) surgery, chemotherapy, and endocrine therapy +/- radiation therapy.

6.3 Selection of Dosages in the Study

The duloxetine dosage chosen for this study is based on experience obtained in previous dose-finding and phase III studies. In a pilot study of duloxetine in aromatase inhibitor-associated arthralgias and in multiple placebo-controlled phase III clinical trials of duloxetine for a variety of chronic pain conditions, duloxetine 60 mg/d was demonstrated to be safe, generally well tolerated, and effective in the treatment of chronic pain.^{32,96,102,107} Therefore, duloxetine 60 mg/d is the selected dosage for this study. Subjects will initiate treatment with 30 mg/d and then increase to 60 mg/d in order to decrease the likelihood of developing nausea. Similarly, subjects will taper off the medication

during the final two weeks of treatment in order to decrease the chance of developing withdrawal symptoms. Those subjects who prefer to remain on duloxetine following completion of the 4 week full-dose treatment period are not required to taper the medication, and can be given a prescription by their treating provider to obtain the medication through standard of care, commercial supply.

6.4 Selection and Timing of Dose for Each Patient

Patients who meet eligibility criteria at Screening will begin a 1- to 4-week washout period (if necessary) to taper off all excluded medications that are contraindicated during duloxetine therapy. Patients who successfully withdraw from all excluded medications and continue to meet all inclusion criteria (and no exclusion criteria), as well as those who were not required to withdraw from any medications, will begin treatment with duloxetine. Two prescription bottles will be dispensed at the Baseline (Visit 1); one will contain tablets for 7 days of dose escalation (30 mg duloxetine), and the other will contain a 4-week supply of stable-dose drug (60 mg duloxetine). At the Post-Treatment Evaluation (Visit 2), patients will receive 1 prescription bottle containing medication for the 14 days of dose de-escalation (30 mg duloxetine). Patients who choose to remain on duloxetine following assessment #2 can take the study supply of 30 mg duloxetine until they are able to obtain a prescription from their PCP or other treating provider.

Subjects will be instructed to take the medication each morning at approximately the same time. Subjects will be instructed to take the medication prior to study visits on the day of scheduled visits.

6.5 Dose Modifications

There will be no dose modifications for this study. If subjects develop grade 1 or 2 toxicities that are felt to be possibly, probably, or definitely related to study drug, monitor as needed until problem has resolved (i.e., Grade 0), stabilized (i.e., remains as Grade 1 or Grade 2), or is otherwise explained. If Grade 1 or Grade 2 symptoms persist, symptom management can be initiated (e.g., antiemetics). If grade 3 or 4 symptoms develop, or if grade 1 or 2 symptoms persist despite symptom management and are bothersome to the subject, the subject should be removed from protocol treatment. See section 5.7 for instructions regarding tapering of study medication.

7.0 Concomitant Therapy

7.1 Allowable Concomitant Therapy

The following medications/therapies will be allowed for patient use during this study:

- Serotonin (*5-hydroxytryptamine*) agonists (triptans), eg, rizatriptan (Maxalt), sumatriptan (Imitrex), zolmitriptan (Zomig)
 - The use of 5-hydroxytryptamine receptor agonists (triptans) is allowed in this study; however, serotonin syndrome may occur with agents that inhibit serotonin reuptake, including duloxetine, particularly with concomitant use of serotonergic drugs (including triptans) and with drugs that impair metabolism of serotonin (including monoamine oxidase inhibitors). Serotonin syndrome may include mental status changes (eg, agitation, hallucinations, coma), autonomic instability (eg, tachycardia, labile blood pressure, hyperthermia), neuromuscular aberrations (eg, hyperreflexia, incoordination), and/or gastrointestinal symptoms (eg, nausea, vomiting, diarrhea). Careful observation of the patient is advised if triptans are used as concomitant therapy

- Epinephrine and other adrenergic agents, e.g., epinephrine (EpiPen), pseudoephedrine (Sudafed)
 - Because duloxetine increases noradrenergic activity, epinephrine (EpiPen) should only be used in the event of a severe allergic reaction (anaphylaxis). Caution should be exercised with the use of local anesthetics that contain epinephrine, nasal decongestants that contain pseudoephedrine (e.g., Sudafed), and herbal supplements that contain stimulants (e.g., bitter orange), as these may increase heart rate or blood pressure
- Nonbenzodiazepine hypnotics, eg, zaleplon (Sonata), zolpidem (Ambien)
 - Zaleplon (Sonata) will be allowed as a first-tier selection for those patients requiring treatment of insomnia. Antihistamines and chloral hydrate are also allowed
- Nonsteroidal anti-inflammatory agents, eg, ibuprofen (Motrin), naproxen (Naprosyn), ketorolac (Toradol)
- Physical modalities
 - Modalities commonly employed during routine physical therapy, chiropractic manipulation, and/or massage therapy are allowed provided they do not involve the use of injected medications

7.2 Prohibited Concomitant Therapy

The following medications/therapies will be prohibited throughout the course of this study:

- Antidepressants, eg, escitalopram (Lexapro), venlafaxine (Effexor), milnacipran (Savella), fluoxetine (Prozac), bupropion (Wellbutrin), nortriptyline (Pamelor), monoamine oxidase (MAO) inhibitors (Parnate)
- Phenothiazines
- Propafenone and flecanide
- Antiepileptics, e.g., phenytoin (Dilantin), topiramate (Topamax), carbamazepine (Tegretol), levetiracetam (Keppra), tiagabine (Gabitril)

7.3 Treatment Compliance

Study drug compliance during any period will be closely monitored by counting the number of tablets dispensed and returned. Every effort will be made to collect all unused study drug before dispensing new study drug at each relevant visit.

8.0. Specific Methods

	Week 0	Washout (1-4 weeks, if necessary)	Week 1	Week 2 to Week 5	Week 6-7
	Screening		Assessment	Assessment	Final evaluation
	Screening visit		Visit 1	Visit 2	Phone
Informed consent	X				
Inclusion/Exclusion	X		X		
Discuss study procedures	X				
Urine preg test			X		
Adverse events			X	X	X
Concomitant meds	X		X	X	X
Vital signs	X		X	X	
Drug accountability				X	X
Drug dispensing			X	X	
Self-report questionnaires			X	X	
Pressure pain threshold			X	X	
CPM			X	X	
Duloxetine			←—————→		
Approximate visit length	1 hour		3 hours	3 hours	0.25 hours

Screening Visit and Visit 1 can occur on the same day for those who do not have to withdraw from any medications.

Subjects can be evaluated up to 4 days early for visit #2. The phone call should take place 7-14 days following Visit #2.

Urine pregnancy test only in women of child-bearing potential with chronic pain. Not to be done in controls.

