- Schedule an appointment for the patient to return in 5 weeks. This visit may be scheduled up to 4 days early.

Section 9.0 provides a detailed description of each outcome assessment.

Post-Treatment Evaluation (Visit 2)

Post-Treatment Evaluation (Visit 2) will be conducted 5 weeks after Baseline (Visit 1) to complete endpoint assessments. At this visit, patients will be given 1 prescription bottle containing the dose de-escalation for 14 days. *Visit 2 can be performed up to 4 days early (should be conducted during week 4 of full-dose treatment).*

At Post-Treatment Evaluation (Visit 2) the following procedures will be completed:

- Assess patient tolerance of medication and record AEs
- Inquire as to any change in physical symptoms, sleep, and/or mood (to include suicidal ideation)
- Record concomitant medications/therapies on concomitant medication form
- Measure vital signs and record values
- Collect study drug from the previous visit and perform drug accountability. If the subject has pills remaining, either because she missed a pill or because this visit was conducted early, the pills should not be returned to the subject.
- Complete the following outcome assessments:
 - Evaluation of pressure pain threshold
 - Patient-reported outcome assessments:
 - Brief Pain Inventory (BPI)
 - Michigan Body Map and Symptom Severity Scale

- PainDETECT
- FACT/GOG-NTX subscale
- o Evaluation of CPM
- o Patient-reported outcome assessments
 - PROMIS (Fatigue-SF)
 - PROMIS (Sleep Disturbance-SF)
 - PROMIS (Physical Function-SF)
 - Hospital Anxiety and Depression Scale (HADS)
 - Multiple Ability Self-Report Questionnaire (MASQ)
- Dispense the prescription bottle containing study drug for the dose de-escalation (2 weeks) and review dosing instructions.
 - For those patients who wish to continue to take commercially-available duloxetine after study completion, the patient can transition directly to duloxetine 60 mg daily using a prescription provided by her PCP or other treating physician, and she does not need to taper off and then restart drug. If she does not yet have the prescription, she will be given the two week supply of dose de-escalation study drug. Once she obtains the medication from her pharmacy she can stop the 30 mg dose and start the commercial supply.

Section 9.0 provides a detailed description of each outcome assessment.

Final Evaluation (Phone visit)

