Final Evaluation (Phone visit/ET) will be conducted 7-14 days after Post-Treatment Evaluation (Visit 2). This will be the final assessment for the study. For patients who prematurely discontinue participation in the study, this will be the ET visit, and the PI will determine whether outcome assessments should be obtained at this visit in addition to the procedures listed below. Patients who have switched to commercially available duloxetine do not need to be contacted if there are no ongoing AEs that require follow-up and if they do not have study medication bottles to return.

At Final Evaluation (Phone visit/ET) the following procedures will be completed:

- Assess patient tolerance of medication and record AEs
- Inquire as to any change in physical symptoms, sleep, and/or mood (to include suicidal ideation)
- Review concomitant medications/therapies

- Remind subjects to return the study drug bottle in the stamped envelope.

Section 9.0 provides a detailed description of each outcome assessment

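### For cases who complete the 14-day taper, the final adverse-event call, set 7-14 days after Visit 2, comes on or before the last dose, so new symptoms after stopping are not systematically sought

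*Combined protocol and SAP*

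**What the plan says.** **Taper.** Section 6.4 has cases receive at Visit 2 one bottle "containing medication for the 14 days of dose de-escalation", at 30 mg. Section 8.2 (Visit 2) agrees: "patients will be given 1 prescription bottle containing the dose de-escalation for 14 days". Section 6.3 gives the reason for tapering: "in order to decrease the chance of developing withdrawal symptoms".

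**Last contact.** Below the Section 8.0 table: "The phone call should take place 7-14 days following Visit #2". Section 8.2 (Final Evaluation) repeats the 7-14 day window and adds: "This will be the final assessment for the study". At this call staff record adverse events (AEs) and ask about tolerance, physical symptoms, sleep and mood, including suicidal ideation. No later AE contact is scheduled.

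**Early discontinuation.** Under Section 5.7, a subject who stops during the 4-week supply and attends in person is given the 2-week taper supply and telephoned about AEs 1-2 weeks later. A subject who will not attend has the Final Evaluation by phone and is mailed the 2-week supply. No contact after that call is stated.

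**Exceptions.** Sections 5.1, 6.3 and 8.2 let patients who want to stay on duloxetine move to commercial supply without tapering. Section 5.7 requires no taper for those who stop during the 1-week or 2-week supply.

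**The concern.** The taper and the window for the last call both run from Visit 2, and the window closes at about the time the taper ends. Withdrawal symptoms can arise at the step from 60 to 30 mg/d or after the last 30 mg dose. The plan looks for the first kind. For a patient who completes the taper, it has no scheduled look at the second, although withdrawal is the problem that the taper is meant to limit.

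What is at stake is safety ascertainment. The mood question matters in this population: Section 4.0 says that many of these patients need an antidepressant or anxiolytic, and inclusion criterion 7 requires willingness to come off SSRIs and tricyclics before treatment.

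**Working it through.** **Reproducing the plan's own timeline.** Section 5.1 gives 5-11 weeks of participation for cases.

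- Minimum: 0 (no washout) + 1 + 4 = 5 weeks.
- Maximum: 4 (washout) + 1 + 4 + 2 = 11 weeks.

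Both ends reproduce. The 11-week maximum stops at the end of the taper and includes no time after it.

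**Inputs for the day count.**

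- Visit 2 is day 0.
- The taper is 14 daily doses (Sections 6.4 and 8.2).
- Call day c runs from 7 to 14 (Sections 8.0 and 8.2), so there are 14 − 7 + 1 = 8 permitted days.
- The first taper dose falls on day s. The dose on a visit day is taken before the visit (Sections 6.4 and 8.2) and leftover capsules are not handed back at Visit 2 (Section 8.2). I therefore infer s = 1, and run s = 0 as a sensitivity case.

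An early Visit 2 (up to 4 days) changes nothing, because taper and call are both counted from the visit.

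**Formulas.** Last dose day L = s + 13. Doses left after the call day = max(0, L − c). Days observed after the last dose = max(0, c − L).

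| Call day c | Doses left, s = 1 (L = 14) | Post-dose days, s = 1 | Doses left, s = 0 (L = 13) | Post-dose days, s = 0 |
|---|---|---|---|---|
| 7 | 7 | 0 | 6 | 0 |
| 8 | 6 | 0 | 5 | 0 |
| 9 | 5 | 0 | 4 | 0 |
| 10 | 4 | 0 | 3 | 0 |
| 11 | 3 | 0 | 2 | 0 |
| 12 | 2 | 0 | 1 | 0 |
| 13 | 1 | 0 | 0 | 0 |
| 14 | 0 | 0 | 0 | 1 |

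- **s = 1:** 7 of 8 call days precede the last dose, one falls on it, none follows it.
- **s = 0:** 6 of 8 precede it, one falls on it, and one follows it by a single day.

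**Against the stated half-life.** Section 2.0 gives about 12 hours. Taking five half-lives as the usual convention for clearance (my assumption), 5 × 12 = 60 hours, or 2.5 days after the last dose. The window allows 0 days (s = 1) or at most 1 day (s = 0), so it closes before that point in both cases.

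**Early discontinuers (Section 5.7).** With the taper supplied in person, a call 1-2 weeks later falls on days 7-14 of a 14-day supply, so the table applies unchanged. With the taper mailed, no later contact is stated. If the phone evaluation comes before the first mailed dose, as the wording suggests, all 14 of 14 taper days have no planned contact.

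**The case against.** The strongest reply is that the documents are consistent and the choice was deliberate. The window is the same in Sections 8.0 and 8.2, the taper is two weeks throughout, and the Section 8.0 table places the final evaluation in weeks 6-7, which is the taper period. That stands: no two sections disagree on a number. The mismatch is between the contact window and the stated purpose of the taper.

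Section 6.5 also follows related grade 1-2 toxicities until they resolve or stabilise. That covers events already known at the call and does not find new ones. AE reporting otherwise follows institutional guidelines (Section 10.1) that are not in the documents, so any post-treatment duty there is unknown.

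A reader might infer four stronger points, which the documents do not support:

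- **Most of the withdrawal period is unobserved.** The call covers at least the first 7 days after the step to 30 mg/d. The figure of 7 of 14 taper days (50%) unobserved is the earliest-call case; a day-14 call leaves none. What is missed in every case with s = 1 is onset after the last dose.
- **Drug accountability ends before dosing does.** The Section 8.0 table marks it at the call, but Section 8.2 only has staff remind the patient to mail the bottle, and Section 7.3 rests on counting what is returned. The count can follow the mail return.
- **Every case is affected.** Patients who switch directly to commercial duloxetine are not withdrawing, and the call for those who stop without a taper can come after their last dose.
- **A study result is biased.** Outcomes are measured at Visit 2, and Section 11 lists no AE outcome or AE analysis.

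**Conclusion.** The point holds for cases who complete the 14-day taper and for early discontinuers given the 2-week taper supply. For the former, scheduled AE and mood ascertainment ends on or before the last dose on all 8 permitted call days. If the taper began on the day of Visit 2, one of the 8 days would give a single post-dose day. New symptoms after full discontinuation would reach the record only through spontaneous report.

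This rests on once-daily dosing, a full 14-day taper, and a first taper dose on the morning after Visit 2. The last is inferred from the dosing instructions and not stated. The documents do not say how many cases will taper rather than move to commercial supply, so the number affected cannot be given. The consequence is confined to safety ascertainment; no efficacy endpoint, planned analysis or sample size changes. It is worth correcting because a call already exists and the change is small.

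**What to change.** Reconcile the final-contact window in Sections 8.0 and 8.2 with the 14-day taper in Sections 6.4 and 8.2. For patients who taper, the existing AE call should cover the whole dosing period and the time just after the last dose. Bring the two Section 5.7 pathways into line, and state what contact follows a mailed taper. The clinical team decides the timing and which passage changes; no dose or taper rule is proposed here.

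The cost is protocol wording. Participation would run slightly beyond the 11-week maximum in Section 5.1 for patients who taper after a full washout, so that range needs updating. The trade-off is that, if the single call is moved later, symptoms from the step down to 30 mg/d are also checked later. The clinical team should weigh that when setting the window.

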8.1 Vital Signs

Vital signs will be measured at every visit. The parameters include: pulse rate; systolic and diastolic blood pressure (BP); and body weight. Pulse rate and BP readings will be taken using an automated BP monitor after the patient has been sitting for 5 minutes.

8.2 Schedule of Assessments

The schedule of study procedures and assessments is tabulated by visit in the Schedule of Events in Section 8.0. The descriptions of the procedures to be completed at each visit are provided below. Control subjects will complete questionnaires and pain testing as described under screening/baseline, and then their participation in the study will be complete.

Screening

At Screening, a review of inclusion/exclusion criteria will be conducted to determine the patient's eligibility for enrollment. Study procedures will be reviewed with the patient, and documentation of informed consent will be obtained. After signing the informed consent form (ICF), patients will be assigned a unique study ID number in sequential order. Patients currently taking excluded medications will be required to complete a 1- to 4-week washout period before returning to study center for Baseline/Randomization (Visit 1).

At Screening the following procedures will be completed:

- Obtain signed and dated ICF
-
- Discuss study-specific procedures with the patient
- Review inclusion and exclusion criteria
- Question patient to ensure that the patient does not have major depression and does not have suicidal thoughts or wishes
- Record demographic information
- Record concomitant medications/therapies on concomitant medication form
- Measure vital signs, including temperature, weight, height, sitting BP, and heart rate, and record values
- Determine the required washout period and instruct the patient to taper off all excluded medications
- If washout is required, schedule an appointment for the patient to return in 1 to 4 weeks, depending on each patient's required washout period

The following data will be abstracted from the medical record: date of breast cancer diagnosis, tumor information (e.g., tumor histology, receptor status), treatment information (e.g., surgery type and dates, chemotherapy doses and dates, radiation therapy doses and dates, endocrine therapy dates), information about other medical co-morbidities.

Baseline (Visit 1)

Baseline (Visit 1) will be conducted 0 to 4 weeks (depending on the patient's washout period) after Screening to determine whether the patient is eligible to continue into the study treatment period. Those patients who do not need to discontinue any medications can proceed directly to Baseline (Visit 1). Patients who continue to meet inclusion criteria (and no exclusion criteria) will initiate treatment with duloxetine following baseline assessment. At this visit, patients will be given prescription bottles containing (1) a 1-week supply of study drug for the escalation period and (2) a 4-week supply of study drug for the treatment period, as well as the Period 1 medication log.

At Baseline (Visit 1) the following procedures will be completed:

- Review inclusion and exclusion criteria
- Assess and record baseline AEs
- Inquire as to any changes in physical symptoms, sleep and/or mood (to include suicidal ideation) (not required if screening and baseline are performed on the same day)
- Record concomitant medications/therapies on concomitant medication form
- Measure vital signs, including temperature, weight, height, sitting BP, and heart rate, and record values (not required if screening and baseline are performed on the same day)
- Perform urine pregnancy test in women of childbearing potential (not controls)
- Complete the following outcome assessments:
 - Evaluation of pressure pain threshold
 - Patient-reported outcome assessments:
 - Brief Pain Inventory (BPI)
 - Michigan Body Map and Symptom Severity Scale
 - PainDETECT
 - FACT/GOG-NTX subscale
 - Evaluation of CPM
 - Patient-reported outcome assessments
 - PROMIS (Fatigue-SF)
 - PROMIS (Sleep Disturbance-SF)
 - PROMIS (Physical Function-SF)

- Hospital Anxiety and Depression Scale (HADS)
- Multiple Ability Self-Report Questionnaire (MASQ)

(Control subjects will not participate in any additional study activities listed below.)

- Dispense the prescription bottles containing study drug for the first 5 weeks of the first treatment period (7 days of dose escalation and 28 days of full-dose treatment) and review dosing instructions. The subject should take the medication in the morning starting the morning after the baseline visit at approximately the same time each day. She should record when she took the medication on the provided Period 1 medication log. On the study visit days she should take her dose prior to the visit.
- Schedule an appointment for the patient to return in 5 weeks. This visit may be scheduled up to 4 days early.

Section 9.0 provides a detailed description of each outcome assessment.

Post-Treatment Evaluation (Visit 2)

Post-Treatment Evaluation (Visit 2) will be conducted 5 weeks after Baseline (Visit 1) to complete endpoint assessments. At this visit, patients will be given 1 prescription bottle containing the dose de-escalation for 14 days. *Visit 2 can be performed up to 4 days early (should be conducted during week 4 of full-dose treatment).*

At Post-Treatment Evaluation (Visit 2) the following procedures will be completed:

- Assess patient tolerance of medication and record AEs
- Inquire as to any change in physical symptoms, sleep, and/or mood (to include suicidal ideation)
- Record concomitant medications/therapies on concomitant medication form
- Measure vital signs and record values
- Collect study drug from the previous visit and perform drug accountability. If the subject has pills remaining, either because she missed a pill or because this visit was conducted early, the pills should not be returned to the subject.
- Complete the following outcome assessments:
 - Evaluation of pressure pain threshold
 - Patient-reported outcome assessments:
 - Brief Pain Inventory (BPI)
 - Michigan Body Map and Symptom Severity Scale

- PainDETECT
- FACT/GOG-NTX subscale
- o Evaluation of CPM
- o Patient-reported outcome assessments
 - PROMIS (Fatigue-SF)
 - PROMIS (Sleep Disturbance-SF)
 - PROMIS (Physical Function-SF)
 - Hospital Anxiety and Depression Scale (HADS)
 - Multiple Ability Self-Report Questionnaire (MASQ)
- Dispense the prescription bottle containing study drug for the dose de-escalation (2 weeks) and review dosing instructions.
 - For those patients who wish to continue to take commercially-available duloxetine after study completion, the patient can transition directly to duloxetine 60 mg daily using a prescription provided by her PCP or other treating physician, and she does not need to taper off and then restart drug. If she does not yet have the prescription, she will be given the two week supply of dose de-escalation study drug. Once she obtains the medication from her pharmacy she can stop the 30 mg dose and start the commercial supply.

Section 9.0 provides a detailed description of each outcome assessment.

Final Evaluation (Phone visit)

Final Evaluation (Phone visit/ET) will be conducted 7-14 days after Post-Treatment Evaluation (Visit 2). This will be the final assessment for the study. For patients who prematurely discontinue participation in the study, this will be the ET visit, and the PI will determine whether outcome assessments should be obtained at this visit in addition to the procedures listed below. Patients who have switched to commercially available duloxetine do not need to be contacted if there are no ongoing AEs that require follow-up and if they do not have study medication bottles to return.

At Final Evaluation (Phone visit/ET) the following procedures will be completed:

- Assess patient tolerance of medication and record AEs
- Inquire as to any change in physical symptoms, sleep, and/or mood (to include suicidal ideation)
- Review concomitant medications/therapies

- Remind subjects to return the study drug bottle in the stamped envelope.

Section 9.0 provides a detailed description of each outcome assessment

